5.3.1 Analysis of OSS if full trial is not feasible

If a trial is not deemed feasible the primary analysis will investigate mean differences in OSS between the treatment arms at each follow-up time point on an intention to treat basis.

The analysis will use a mixed-effects repeated measures model with restricted maximum likelihood estimation. Patient level random effects will not be specified. Instead, an unstructured covariance matrix for the residual errors will be used to model correlation within repeated measures.⁹ Observations from different participants are assumed independent. Satterthwaite approximation for degrees of freedom will be used to avoid upward bias of type I error due to the relatively small sample size.¹⁰⁻¹¹ Gender, age, site and baseline OSS will be adjusted for in the model as fixed effects. An interaction effect between post-randomisation time point (as a categorical variable) and baseline OSS will be fitted. An interaction effect between the randomised treatment group and post-randomisation time point will also be fitted to allow for a saturated model for the mean at each time point for each treatment group.⁹ Missing baseline OSS scores will be imputed using mean imputation.

ROM and EQ-5D will be analysed using the same mixed-effects model as specified for OSS or an equivalent model appropriate for the outcome type.

Strategy for analysis of clinical outcomes if full trial is not feasible and if the above model fails to converge:

1. Remove interaction effects between visits and baseline OSS
2. Remove fixed effect gender
3. Remove fixed effect age
4. Remove fixed effect Site
5. Remove main fixed effect baseline OSS
6. Forgo mixed-effects repeated measures model and adopt simple between group t-tests at each time point

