Table 14 Adjusted treatment effects on OSS, EQ-5D-3L summary index, and ROM at post-randomisation time points if full trial is deemed infeasible.

	V3 (N=)	V4 (N=)	V5 (N=)
OSS			
Treatment - n/N (%)			
Control – n/N(%)			
Adjusted difference in mean OSS between treatment groups* - 95% confidence interval (CI)			
p-value			
EQ-5D-3L Summary Index			
Treatment - n/N (%)			
Control – n/N (%)			
Adjusted difference in mean EQ-5D-3L summary index between treatment groups* - 95% confidence interval (CI)			
p-value			
ROM			
Treatment - n/N (%)			
Control – n/N (%)			
Adjusted difference in mean ROM between treatment groups* - 95% confidence interval (CI)			
p-value			

*Direction of difference: treatment group mean – control group mean. Difference is adjusted for fixed effects (site, age, gender, baseline OSS) and interaction effects between baseline measurements and visits.

Table 15: Total number of AEs by treatment groups and overall

	Intervention (N=)	Control (N=)	Overall (N=)
Overall			
Complications/Expected AE			
Pain at injection site			
Cutaneous infection at injection site			
Loss of subcutaneous fat at injection site causing a skin dimple.			
Steroid flare (transient significant increase of pain symptoms lasting usually no more than 72 hours)			
Disturbance of menstrual cycle			
Transient weakness in arm muscles caused by local anaesthetic leaking around nerves and having a temporary numbing effect lasting no more than a couple of hours			
Significant disturbance in blood sugar level in diabetic patients due to administration of corticosteroid			
Development of septic arthritis due to the introduction of infection to the shoulder joint following injection			
Unexpected AE			

Table 16: Number and proportion of patients with at least 1 AE overall and in each treatment group by study visits

	Intervention (N=)	Control (N=)	Overall (N=)
Overall			
Injection visit			
V3			
V4			
V5			

Table 17: Total number of SAEs by treatment groups and overall

	Intervention (N=)	Control (N=)	Overall (N=)
Overall			
Death			
Life-threatening			
Requires in patient hospitalisation or prolongation of hospitalisation			
Results in significant disability or incapacity			
Congenital anomaly or birth defect			
Requires intervention to prevent permanent impairment			
Deemed by the PI to be medically significant			
Other important medical event			

Table 18: Number and proportion of patients with at least 1 SAE overall and in each treatment group by study visits

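### If the full trial is judged infeasible, the EQ-5D and ROM models name only baseline OSS as baseline outcome covariate, not each outcome's own baseline

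*SAP*

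**What the plan says.** Section 5.3.1 applies only if the full trial is not deemed feasible. It sets out a repeated-measures model for OSS with these covariates: "Gender, age, site and baseline OSS will be adjusted for in the model as fixed effects". It adds a baseline-by-visit term: "An interaction effect between post-randomisation time point (as a categorical variable) and baseline OSS will be fitted". The model is then extended to the other outcomes: "ROM and EQ-5D will be analysed using the same mixed-effects model as specified for OSS or an equivalent model appropriate for the outcome type".

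Three other places bear on which baseline is meant:

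- The non-convergence list in 5.3.1 is introduced as covering the clinical outcomes. Its first and fifth steps drop baseline OSS terms, and no other baseline outcome appears in it.
- The mean-imputation sentence in 5.3.1 deals with missing baseline OSS only.
- The Table 14 footnote names the main effects: "Difference is adjusted for fixed effects (site, age, gender, baseline OSS"). Its full sentence reads "Difference is adjusted for fixed effects (site, age, gender, baseline OSS) and interaction effects between baseline measurements and visits". Its asterisk stands on the OSS row and on the other two: "Adjusted difference in mean EQ-5D-3L summary index between treatment groups* - 95% confidence interval (CI") and "Adjusted difference in mean ROM between treatment groups* - 95% confidence interval (CI").

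Baseline EQ-5D, forward flexion and external rotation are all collected. They appear in the Section 3.2 schedule, the Section 5.1 baseline list and dummy Tables 5 and 6. Sections 3.2 and 5.3 treat flexion and external rotation as separate outcomes, but Table 14 has one ROM row.

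**The concern.** An outcome's own baseline is usually its best available predictor. Adjusting EQ-5D or ROM for baseline OSS in its place keeps a probably weaker predictor and omits a probably stronger one that is already in the database. Two things follow. The confidence intervals are wider than they need to be. And a chance difference between arms in baseline EQ-5D or ROM is removed only to the extent that it runs along with baseline OSS, although the result is labelled an adjusted difference.

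Table 14 gives confidence intervals and p-values for these outcomes, and this is the one situation in which Section 5.3 permits significance testing. The covariate set should therefore be unambiguous before the analysis.

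**Working it through.** **Stated figure.** The SAP gives no SD, correlation, effect size or power for EQ-5D or ROM, so there is no figure of its own to reproduce.

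**Inputs from the SAP.** There are 66 participants (Section 4.1). Allocation is 1:1:1:1 (Section 4.2), which is 1:1 for the treatment comparison, or 33 per arm. Attrition of 15% is stated for the definitive trial (Section 4.1) and is borrowed here as an assumption: 66 × 0.85 = 56 analysed.

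**Assumed inputs.** Correlation of own baseline with follow-up, r_own: 0.3 to 0.7. Correlation of baseline OSS with follow-up of the outcome, r_oss: 0.1 to 0.4, never above r_own. Correlation between the two baselines, r_b: 0.3 to 0.5.

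**Precision.** This uses a single-visit analysis-of-covariance approximation, with SE in SD units = √[(1 − r²) × 4/n]. The variance ratio, baseline OSS against own baseline, is (1 − r_oss²)/(1 − r_own²).

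| r_own | r_oss 0.1 | r_oss 0.2 | r_oss 0.3 | r_oss 0.4 |
|---|---|---|---|---|
| 0.3 | 1.09 | 1.05 | 1.00 | not considered |
| 0.5 | 1.32 | 1.28 | 1.21 | 1.12 |
| 0.7 | 1.94 | 1.88 | 1.78 | 1.65 |

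At r_own = 0.5 and r_oss = 0.3 the ratio is 0.91/0.75 = 1.21. The SE is √(0.91 × 4/56) = 0.255 with baseline OSS and √(0.75 × 4/56) = 0.231 with own baseline, so intervals are about 10% wider (√1.21 = 1.10). At the extremes, 0.91/0.91 = 1.00 and 0.99/0.51 = 1.94.

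**Chance imbalance.** With 33 per arm, the SD of a baseline difference is √(2/33) = 0.25 SD. Suppose the own baseline differs by 0.25 SD while baseline OSS happens to be balanced. The OSS-adjusted difference then shifts by 0.25 × (r_own − r_oss × r_b)/(1 − r_b²). At r_own = 0.5 and r_oss = 0.3:

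- r_b = 0.3: 0.25 × 0.41/0.91 = 0.113 SD
- r_b = 0.5: 0.25 × 0.35/0.75 = 0.117 SD

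Over the whole assumed range the shift is 0.05 to 0.22 SD.

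If baseline OSS moves with the own baseline as their correlation predicts, the adjustment helps somewhat. Without adjustment the expected shift is 0.25 × 0.5 = 0.125 SD. With baseline OSS it is 0.25 × (0.5 − 0.3 × r_b), which is 0.103 SD at r_b = 0.3 and 0.088 SD at r_b = 0.5. The correction is real but partial.

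**The case against.** The strongest reply is that the authors may well have meant own baselines. Section 5.3.1 allows an equivalent model suited to the type of outcome, and using the same model for a new outcome can naturally mean swapping in that outcome's baseline too. The footnote moves from baseline OSS in its list of main effects to plural baseline measurements in its interaction term. If that plural means each outcome's own baseline, its interaction with a categorical visit would carry the own-baseline effect at every visit.

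This stands as far as intent goes. A reader might infer that the plan has deliberately chosen baseline OSS over the own baseline, and the text does not prove that. But neither phrase says that own baselines are used. Outcome type most naturally refers to the kind of variable. The own-baseline reading of the footnote would pair an own-baseline interaction with a baseline OSS main effect, and it would depart from Section 5.3.1, where the interaction is with baseline OSS. Every explicit mention is of baseline OSS.

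Three further limits stand. The analysis is conditional on infeasibility; otherwise EQ-5D and ROM are only described, and OSS is the proposed primary outcome throughout. Randomisation protects against bias on average. And the calculation ignores age, gender and site, which are in the model, and the repeated measures.

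**Conclusion.** The point holds as a specification weakness in a conditional, secondary analysis. Read as written, the EQ-5D and ROM models adjust for baseline OSS only. This loses precision when the own baseline is the better predictor, and corrects chance imbalance only in part.

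The size is illustrative: a variance ratio of 1.21 at assumed correlations of 0.5 and 0.3, and 1.00 to about 1.9 over the assumed range. There is no loss where baseline OSS predicts the outcome as well as its own baseline does.

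Two stronger readings are tempting and not supported. A reader might infer that baseline imbalance goes wholly uncorrected or that the estimates are biased. Baseline OSS removes the part of the imbalance that it shares, and the estimates are unbiased over repeated randomisations; the harm is lost precision and a shift conditional on the imbalance that occurred. A reader might also turn 1.21 into a fixed loss of participants (1 − 0.75/0.91 = 18%). That percentage depends entirely on correlations that the SAP does not give.

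**What to change.** State that each outcome's model uses that outcome's own baseline value and its interaction with visit: the baseline EQ-5D-3L index for EQ-5D, baseline flexion for flexion, baseline external rotation for external rotation. Keep baseline OSS for the OSS model only. Make the same change in four places so that they agree: the model paragraph of Section 5.3.1, its baseline mean-imputation sentence, its non-convergence list and the Table 14 footnote.

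Replace the single ROM row of Table 14 with separate rows for flexion and external rotation, since one row cannot carry two baselines.

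The cost is SAP wording and one extra table block. No new data are needed, because all three baselines are already collected.

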5.1 Baseline characteristics

Baseline characteristics will be summarised for each treatment group, using mean (SD) and median (IQR) for continuous variables and n (%) for categorical variables.

The baseline variables are:

- Oxford Shoulder Score (OSS)
- Quality of life will be assessed using the Euroqol (EQ-5D-5L)
- Upper limb range of motion (ROM) – forward flexion
- Upper limb range of motion (ROM) – external rotation
- Demographic questions:
 - Age
 - Gender
 - Ethnicity
- Baseline characteristics:
 - Medical history
 - Duration of shoulder pain
 - Smoking and alcohol history

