6.3 Safety analyses

SAE: We will report the total number of serious adverse events (SAEs) related to the ACCorD intervention overall and in each treatment group. We will also report the number of patients with at least one SAE by treatment group at injection visit (visit 2) and at each time point post injection (visit 3, visit 4, and visit 5).

AE: We will report the number of unexpected and expected AEs (complications) in each treatment group. We will also report the number of patients with at least one AE by treatment group at injection visit (visit 2) and at each time point post injection (visit 3, visit 4, and visit 5).

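### Named complications are planned as event totals only, so the plan gives no number or proportion of patients affected by each one

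*SAP*

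**What the plan says.** On adverse events, SAP section 6.3 states: "We will report the number of unexpected and expected AEs (complications) in each treatment group". That is a count of events. The same section adds the number of patients with any adverse event, by arm, at the injection visit and at each later visit.

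The table shells in Appendix 3 follow this text:

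- "Table 15: Total number of AEs by treatment groups and overall" is the only table that lists complications by name. Its columns are intervention, control and overall, each with a single N. No row carries an n/N or a percentage.
- "Table 16: Number and proportion of patients with at least 1 AE overall and in each treatment group by study visits" counts patients. Its rows are overall and the four visits, with every type of event pooled.
- Tables 17 and 18 repeat the pattern for serious adverse events: totals by category in one, patients pooled across categories in the other.

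One row of Table 15 is defined for a subgroup: "Significant disturbance in blood sugar level in diabetic patients due to administration of corticosteroid". Section 5.1 names "Medical history" among the baseline variables to be summarised by treatment group. Table 1 has rows for age, gender, ethnicity, duration of pain, smoking and alcohol, but none for medical history.

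**The concern.** A reader of the safety results will want to know how many people in each arm had a given complication. A total of events does not answer that. A few patients with repeated reports can raise an arm's total, and a total shared among many patients looks the same as one concentrated in a few. The pooled patient count in Table 16 does not separate pain at the injection site from infection, steroid flare or a disturbance in blood sugar.

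The blood-sugar row has a further gap. It concerns diabetic participants only, yet no shell shows how many there are in each arm. A difference between arms in that row could not be set against a difference in the number of people at risk.

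At stake is how informative the descriptive safety tables are, including for whoever designs the definitive trial. No test or primary result depends on it.

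**Working it through.** The plan states no safety rate or risk, so there is no figure to reproduce. The check has three steps.

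**1. Which table gives which count**

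| Output | Unit | By named complication or category? |
|---|---|---|
| Section 6.3, first adverse-event sentence, and Table 15 | events | yes |
| Section 6.3, second adverse-event sentence, and Table 16 | patients | no, all types pooled, by visit |
| Table 17 | serious events | yes |
| Table 18 | patients | no, pooled, by visit |

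No output combines patients with named complication.

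**2. How far events leave patients undetermined**

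Inputs: 66 participants (section 4.1), randomised 1:1:1:1 to four groups, two of which receive each treatment (section 4.2). So each arm has about 66 × 2/4 = 33. The figure of 6 events is an illustration and is not in the plan.

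If *m* patients account for 6 events, *m* can be any whole number from 1 to 6. The proportion affected is *m*/33, with exact (Clopper-Pearson) 95% intervals:

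| Patients affected | Proportion of 33 | 95% CI |
|---|---|---|
| 1 | 1/33 = 3.0% | 0.1 to 15.8% |
| 3 | 3/33 = 9.1% | 1.9 to 24.3% |
| 6 | 6/33 = 18.2% | 7.0 to 35.5% |

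Table 15 would print 6 in each case.

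The overall row of Table 16 narrows this only partly. Let *A* be the patients with any adverse event and *O* the events of all other types. Then *m* lies between the larger of 1 and *A* − *O*, and the smaller of 6 and *A*. If other events are rare, *m* is nearly fixed. If they are common, it is not.

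**3. The diabetic count**

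Section 5.1 commits to summarising medical history by arm, and Table 1 omits it. That is a mismatch between text and shell. The SAP does not say that medical history records diabetes, so whether a diabetic count can be derived is open.

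**The case against.** The case for leaving the plan alone has several sound parts.

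- **Events and patients will often coincide.** Section 2 describes a single injection procedure in each arm. Table 15 itself describes steroid flare as usually over within 72 hours and the arm weakness as lasting a couple of hours at most. Such events will rarely recur in one person. This stands: the gap matters mainly for pain, and perhaps for blood sugar.
- **There is no stated rule for repeat reports.** A reader might infer that a patient who mentions pain at several contacts is counted each time. The SAP does not say so, and the rule may sit in the protocol. The divergence is therefore possible, not established.
- **The pooled count may still be useful.** A reader might infer that nearly everyone will have some adverse event, so that Table 16 could show no difference. No figure in the SAP supports that, and the breakdown by visit separates the injection day from later events.
- **The study is not designed to estimate complication risk.** That risk is absent from the feasibility objectives in section 2 and the outcomes in section 3.1. Section 6.6 names standard deviation, retention, data availability and recruitment as inputs to the full trial. This also stands and limits the importance of the point.
- **The counts could be derived at the reporting stage.** Patient-level adverse-event records would normally allow it. That shows the fix is cheap. It does not change what the plan now promises.

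None of this supplies the missing output. Section 6.3 and its tables agree with one another, and together they leave out patients by complication.

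**Conclusion.** The point holds as a minor fault in descriptive safety reporting. The plan fixes the unit for each named complication as events, counts patients only for all types pooled, and so gives no patient-level frequency for any complication. In the illustration, one printed total is compatible with 3.0% to 18.2% of an arm of about 33. That range assumes 6 events and that repeat reports by one patient are possible.

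Two stronger readings are not supported.

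- A reader might infer that the plan would misstate the blood-sugar risk: 2 affected patients out of 33 is 6.1%, against 2/10 = 20% or 2/5 = 40% among diabetic participants. Table 15 prints no percentage, its N is undefined, and the 5 to 10 diabetic participants per arm are assumed. The comparison is hypothetical. Even the true subgroup figure would be very imprecise: the exact 95% interval for 2/10 is 2.5 to 55.6%.
- A reader might ask for a separate denominator for the row "Disturbance of menstrual cycle". The SAP does not show that menstrual status is collected, so that request should not be made.

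The missing medical-history row in Table 1 is a plain mismatch with section 5.1 and needs no assumption.

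**What to change.** 1. In section 6.3 and Table 15, report for each complication the number of patients with at least one occurrence (n/N, %) beside the number of events, and define N in the column heads.
2. Do the same by category in Table 17.
3. Add to Table 1 the medical-history summary by arm that section 5.1 already lists.
4. If medical history records diabetes, show the number of diabetic participants in each arm beside the blood-sugar row. Present it descriptively, with a note that the denominator is very small.

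The first two changes use patient-level adverse-event records that the trial would normally hold, and the third uses a variable already listed. The fourth depends on what the medical-history form captures. The cost is an edit to one paragraph and three table shells, and a slightly larger Table 15. No test or estimate elsewhere in the plan changes.

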3.1 Feasibility outcomes

The feasibility outcomes measured are:

Recruitment

- The average rate of eligible participants presenting to MSK hubs per month:
 - o No. of eligible participants presenting to MSK hubs during recruitment period/ length of recruitment period (in months)
- Proportion of eligible participants clinicians willing to recruit (see appendix 2 for more detail):
 - o No. of eligible participants clinicians willing to recruit/ no. of eligible participants presented to MSK hubs
- Proportion of eligible participants that are randomised:
 - o No. of eligible participants randomised/ no. of eligible participants presented to clinicians.

Adherences

- Participant adherence to study protocol:
 - o No. of participants receiving injections / no. of randomised participants

Retention

- General retention:
 - o No. of participants who provided any follow-up data / no. of randomised participants for study visits listed in section 3.2, overall and by treatment groups
- Oxford Shoulder Score (OSS) questionnaire retention:
 - No. of participants who answered any OSS items / no. of randomised participants for study visits listed in section 3.2, overall and by treatment groups

Data completeness

- Proportion of missingness in each outcome at each time point (as specified in section 3.2), overall and by reasons of missingness (where available):
 - o No. of participants who provided complete outcome (usable in analysis without imputation)/ no. of randomised participants
- Proportion of randomised participants who returned resource use questionnaire, by study visits, overall and by reason of missingness (where available):
 - o No. of randomised participants who returned resource use questionnaire/ no. of randomised participants for study visits listed in section 3.2 where such a questionnaire is due
- Proportion of randomised participants who were successfully linked to administrative primary care records
 - o No. of randomised participants successfully linked to administrative primary care records/ no. of randomised participants
- Proportion of randomised participants who were successfully linked to administrative hospital care records
 - o No. of randomised participants successfully linked to administrative hospital care records/ no. of randomised participants

Concordance of health care data collected with case report forms against routinely collected linked data

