4.2 Randomisation procedure

Randomisation will only occur when the research team confirms eligibility, and the participant has provided written, informed consent.

Participants will be randomised in a 1:1:1:1 ratio, stratified by recruiting centre, to one of the following:

- CSI&HD and patient to self-measure ROM self-measured before 6 week (+/- 3 days) visit
- CSI&HD and patient to self-measure ROM self-measured after 6 week (+/- 3 days) visit
- CSI alone and patient to self-measure ROM self-measured before 6 week (+/- 3 days) visit
- CSI alone and patient to self-measure ROM self-measured after 6 week (+/- 3 days) visit

The allocation will be determined just prior to the time of the injection, using a web-based, distant randomisation service administered by the Pragmatic Clinical Trials Unit, QMUL. Allocation lists using random permuted blocks of sizes 4 and 8 will be prepared by the trial statistician with the final lists being uploaded to the randomisation system by an independent statistician.

The clinician providing the injection will contact a member of the research team once the participant has arrived for their appointment. The research team member who is appropriately and sufficiently trained and delegated to complete randomisation will randomise the patient and communicate the allocation to the treating clinician.

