5.3 Analysis of clinical and health economics outcomes

Descriptive statistics will be used to summarise all clinical and health economics outcome measures at each time point in each group.

As this is a feasibility study and the sample size is small, there will be no significance testing, except for circumstances described in 5.3.1, where the definitive trial is deemed infeasible.

Complete case analyses are assumed unless otherwise specified.

For Oxford Shoulder Score (OSS):

- Mean (SD) and median (IQR) will be presented for each group at each time point
- Sensitivity analyses will be conducted on mean (SD) and median (IQR) by presenting and comparing statistics derived using different methods of imputation on individual missing items (see 5.6 for more details)
- Percentage of missing will be presented for each group at each time point

For range of motion (ROM) – forward flexion:

- Mean (SD) and median (IQR) will be presented for each group at each time point
- Percentage of missing will be presented for each group at each time point

For range of motion (ROM) – external rotation:

- Mean (SD) and median (IQR) will be presented for each group at each time point
- Percentage of missing will be presented for each group at each time point

For each domain of health-related quality of life (EQ-5D-5L):

- Proportion of participants at each level
- Percentage of missing will be presented for each group at each time point

For health-related quality of life (EQ-5D-5L) summary index:

- Mean (SD) and median (IQR) will be presented for each group at each time point
- If the score for a domain is missing, then the overall index would be treated as missing
- Percentage of missing will be presented for each group at each time point

For health-related quality of life (EQ-5D-5L) VAS score:

- Mean (SD) and median (IQR) will be presented for each group at each time point
- Percentage of missing will be presented for each group at each time point

For cost of resources used (2023£): healthcare costs, personal care costs, time-off-work costs, out-of-pocket costs

- Mean (SD) and median (IQR) will be presented for each group at each time point

- Percentage of missing will be presented for each group at each time point

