6.5 Withdrawal and deviations

Withdrawal: We will report the total number of withdrawals and the reasons for withdrawal overall and by treatment group at each time point. Reasons for withdrawal are specified in table 19 and categorised as follows:

- Withdrawal by PI
- Adverse event related
- Withdrawal by patient
 - Withdrawal by patient for intervention only
 - Withdrawal by patient for the whole study

Protocol deviation: We will report the total number of deviations and the types of deviations overall and by treatment group and site. The types of deviations are specified in table 21 and categorised as follows:

- Data deviation
- Deviation in consent
- Randomisation deviation
- Intervention deviation
- Follow-up deviation
- Others

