	Intervention (N=)	Control (N=)	Overall (N=)
Overall			
Injection visit			
V3			
V4			
V5			

Table 19: Reasons for withdrawal overall and by treatment group

	Intervention (N=)	Control (N=)	Overall (N=)
Overall			
Withdrawal by PI			
Adverse event related			
Withdrawal by patient			
Withdrawal by patient for intervention only (data will be collected up to date of withdrawal)			
Withdrawal by patient for whole study			

Table 20: Number and proportion of withdrawals overall and by treatment group at each time point

	Intervention (N=)	Control (N=)	Overall (N=)
Overall			
V1/Baseline			
V2/ Injection Visit			
V3			
V4			
V5			

Table 21: Number and types of deviations overall and by site

	Tower Hamlets	Newham	Waltham Forest	Cambridgeshire and Peterborough	Overall
Overall					
Data deviation					
Deviation in consent					
Randomisation deviation					
Intervention deviation					
Follow-up deviation					
Others					

Table 22: Number and types of deviations overall and by treatment groups

	Intervention	Control	Overall
Overall			
Data deviation			
Deviation in consent			
Randomisation deviation			
Intervention deviation			
Follow-up deviation			
Others			

Table 23: Participant experience questionnaire overall and by treatment groups

	Intervention (N=) – n/N (%)	Control (N=) – n/N (%)	Overall (N=) – n/N (%)
Participation Questionnaire			
The participant information sheet was easy to understand			
Strongly Agree			

Agree			
Neutral			
Disagree			
Strongly Disagree			
Missing			
Education information/booklet about managing frozen shoulder was easy to understand			
Strongly Agree			
Agree			
Neutral			
Disagree			
Strongly Disagree			
Missing			
Education about managing frozen shoulder was helpful in my recovery			
Strongly Agree			
Agree			
Neutral			
Disagree			
Strongly Disagree			
Missing			
The process of speaking with the research team about the study before I joined was helpful			
Strongly Agree			
Agree			
Neutral			
Disagree			
Strongly Disagree			
Missing			
The consent process was easy to understand and complete			
Strongly Agree			
Agree			
Neutral			
Disagree			
Strongly Disagree			
Missing			
I enjoyed participating in the study			
Strongly Agree			
Agree			
Neutral			
Disagree			

Strongly Disagree			
Missing			
I would participate in another research study in the future			
Strongly Agree			
Agree			
Neutral			
Disagree			
Strongly Disagree			
Missing			
Experience on attending study visits			
Visit1 - Baseline			
Face-to-face			
Phone			

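### The SAP's Table 19 stops data collection for participants who withdraw from the intervention only, so for outcome data they become the same as whole-study withdrawals

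*SAP*

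**What the plan says.** Section 6.5 splits withdrawal by the patient into two kinds, "Withdrawal by patient for intervention only" and withdrawal from the whole study, and says nothing about data collection for either. Table 19 in Appendix 3 repeats the split and adds a data rule to one row: "Withdrawal by patient for intervention only (data will be collected up to date of withdrawal"). The companion row, "Withdrawal by patient for whole study", has no note. Nowhere else does the SAP say whether participants who give up only the intervention remain in follow-up.

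Four other parts of the SAP bear on this:

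- Section 3.1 defines adherence as "No. of participants receiving injections / no. of randomised participants" and general retention as "No. of participants who provided any follow-up data / no. of randomised participants", the latter by study visit. These are separate feasibility outcomes with the same denominator.
- Section 4.2 places randomisation immediately before treatment: "The allocation will be determined just prior to the time of the injection".
- Section 5.3 sets the default for clinical outcomes: "Complete case analyses are assumed unless otherwise specified". If a full trial is not deemed feasible, section 5.3.1 estimates "mean differences in OSS between the treatment arms at each follow-up time point on an intention to treat basis".
- Section 6.6 uses retention and data availability from this study to size the definitive trial.

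**The concern.** Separating withdrawal from treatment from withdrawal from the study is useful mainly because the first group can still be followed up. A data cut-off on the intervention-only row removes that use. A refusal of the injection, which is an adherence matter, then also becomes a loss to follow-up.

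Retention, data completeness and the attrition allowance for the definitive trial are among the quantities this study exists to estimate. If part of the observed attrition comes from the study's own decision to stop collecting data, the estimate does not describe what a trial that follows everyone up would achieve. If the 5.3.1 comparison is run, participants who gave up the intervention would belong to their allocated arm but have no outcome to analyse.

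**Working it through.** The SAP states no figure for this point. The check is a reading of the text followed by simple arithmetic.

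**What the rule does to one participant**

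1. Allocation is made just before a single injection visit (4.2). A randomised participant who gives up only the intervention would normally do so between allocation and the end of that visit. Someone who leaves before allocation is in none of the denominators.
2. Outcome visits after treatment are at 6, 12 and 26 weeks (3.2). If data stop at the withdrawal date, usually only baseline data exist.
3. Retention (3.1): no follow-up data, so not retained at any of the three visits.
4. Adherence (3.1): if the injection was not given, the same person is also non-adherent.
5. Complete-case summaries (5.3): absent at every follow-up visit.
6. Repeated-measures model (5.3.1): baseline OSS is a covariate and the outcomes are the post-randomisation scores, so the participant contributes no outcome.
7. A whole-study withdrawal at the same moment gives the same result in steps 2 to 6. For outcome data the two rows of Table 19 are therefore identical.

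**Size per case**

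Inputs: 66 participants (4.1). Randomisation is 1:1:1:1 over four groups, two per treatment (4.2), so about 66/2 = 33 per arm.

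- Overall: 1/66 = 1.5 percentage points of retention at each follow-up visit.
- Within an arm: 1/33 = 3.0 percentage points.

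These are upper values, since they suppose the participant would otherwise have been retained. With the SAP's 15% attrition estimate (4.1) applied to that participant too, the expected overall loss is 0.85/66 = 1.3 points.

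**Carry-over to the definitive trial (illustration)**

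Let k be the number of intervention-only withdrawals among the 66. The SAP gives no value, so k is an assumption. Other attrition is taken as 15%. The SAP's 448 including attrition implies about 448 × 0.85 = 380.8 analysable participants. Using 380, 380/0.85 rounds up to 448, which reproduces the stated number.

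- Retention if they are followed up: 0.85 × 66/66 = 85.0%, N = 448.
- Retention if data stop: 0.85 × (66 − k)/66, and N = 380 divided by that, rounded up.

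| k (assumed) | Retention if data stop | Apparent attrition | Definitive-trial N |
|---|---|---|---|
| 0 | 85.0% | 15.0% | 448 |
| 2 | 82.4% | 17.6% | 462 |
| 5 | 78.6% | 21.4% | 484 |

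The increases of 14 and 36 participants would come from the data rule alone.

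**The case against.** The basis is thin. The rule is a parenthesis in a dummy-table row label, and section 6.5, which the table serves, contains no such rule. Follow-up after withdrawal is commonly set in the protocol, which was not available here, and the note may simply sit on the wrong row. This stands as a reason for caution about what is done in practice. It does not remove the need for correction: a misplaced note is still wrong, and it is the only statement on the matter in the SAP.

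Numbers should also be small. There is one injection and a short interval between allocation and treatment. This stands too, and it limits the size of the point.

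A reader might infer more than the SAP supports:

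- **That the rule contradicts intention to treat.** Participants stay in their allocated arm, but their outcomes are missing. That weakens the analysis without contradicting the principle, and the 5.3.1 analysis is conditional on a full trial not being deemed feasible.
- **That data will be lost unequally by arm because hydrodilatation may be poorly tolerated.** The intervention description treats poor tolerance as a reason to cease the saline, with the volume recorded. It does not class it as withdrawal, and the participant has still received an injection. Participants are blinded and allocation immediately precedes treatment, so refusal before the injection has no evident reason to depend on arm.
- **That every non-adherent participant is lost to retention.** Table 19 has separate rows for withdrawal by the PI and for adverse events, and an injection may be missed without any formal withdrawal. The note covers one row.
- **That section 6.2 commits the analysis to outcomes after treatment is given up.** Treatment policy is listed there only as one candidate among several, and withdrawal from the intervention is not a listed intercurrent event.
- **That a bias in mean OSS can be quantified.** The SAP gives neither a count of such withdrawals nor a difference in their scores.

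**Conclusion.** The point holds as a defect in a stated rule. Taken literally, Table 19 ends data collection for intervention-only withdrawals, and nothing else in the SAP overrides it. The firm consequences are for retention, data availability and the attrition carried into 6.6, and these apply whether or not a full trial is judged feasible. The loss to the intention-to-treat comparison arises only if 5.3.1 is triggered.

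The size is at most 1.5 points of overall retention per case, or about 3 points in an arm. This assumes 33 per arm and withdrawal before or around the injection. The total effect depends on a count that the SAP does not give and that is probably low. The illustrative sample sizes of 462 and 484 rest on assumed counts of 2 and 5 and are not predictions.

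**What to change.** In section 6.5 and Table 19, state that participants who withdraw from the intervention only remain in follow-up with their agreement, and that their data count towards retention and data completeness and, if it is run, the 5.3.1 intention-to-treat analysis. Move the note about collecting data up to the withdrawal date to the whole-study row. Check that the protocol and the withdrawal form say the same.

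If some participants have already had follow-up stopped under the literal rule, report how many, and show retention with and without them before it is used in 6.6.

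The cost is a few lines of SAP wording, possibly a matching change to the withdrawal form, and a small number of follow-up contacts that are already scheduled. Two of the three follow-up visits are remote.
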